### **Aim 3.**

We aim to explore whether changes in self-efficacy, HF knowledge, and/or skills mediate the effect of self-care management.

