Investigation of mediators (SCI-2) will be done by examining whether changes in self-care confidence, self-efficacy to manage symptoms, self-efficacy to manage

medications & treatment, or HF knowledge mediate the effect of the mHealth intervention on patient outcomes (e.g., self-care of HF index). We will use the method proposed by Hayes (2016) for evaluating mediation effects via a regression modeling approach which reflects the change scores in the mediators. Baseline measurement of the potential mediator and baseline outcome measure (e.g., self-care of HF index) will be included as covariates to provide a precise estimate of mediation effects. The test of mediation evaluating the indirect effect of the invention on outcome will be based on a product of coefficients approach. The modeling and testing for mediation as described by Hayes (2016) will be done for each mediator separately. As a sensitivity analysis for the mediation analyses, we plan to use a non-parametric bootstrap approach. Both the indirect effect of each mediator along with 95% bootstrap confidence intervals will be reported.

Sensitivity analyses to determine the impact of key assumptions. In the event that continuous endpoints are skewed or key distributional assumptions are not met, we will investigate transformations (e.g., log) and compare findings based on parametric and non-parametric tests (e.g., Wilcoxon rank-sum test & robust regression techniques), as a sensitivity analysis to confirm findings. To address the impact of missing data, multiple imputation methods will be investigated.

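### Aim 3 tests four mediators one at a time; if they are correlated and the arm moves them all, a scale with no effect can appear to mediate, so a joint model should be reported beside the separate ones

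*Combined protocol and SAP*

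**What the plan says.** Aim 3 is worded as exploration: "We aim to explore whether changes in self-efficacy", knowledge or skills mediate. The mediator paragraph of Data Analysis lists four candidates, "changes in self-care confidence, self-efficacy to manage symptoms, self-efficacy to manage" and then "medications & treatment, or HF knowledge mediate the effect of the mHealth intervention on patient outcomes". Table 1 marks the same four scales as hypothesised mediators, all completed by the patient at baseline, 3 and 6 months. (Skills, named in Aim 3, has no counterpart in this list; that is a separate matter.)

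The model is specified in one sentence: the mediation modelling and tests, following the cited regression method, "will be done for each mediator separately". The test of the indirect effect "will be based on a product of coefficients approach". The covariates are "Baseline measurement of the potential mediator and baseline outcome measure", so the other three mediators do not enter. The only sensitivity analysis named specifically for mediation is a non-parametric bootstrap, and each indirect effect is to be reported with its 95% bootstrap interval. The section gives no joint model, no caveat about overlap between the scales and no inter-mediator correlation. It does not plan to add the indirect effects or to report a proportion mediated.

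**The concern.** In a single-mediator model the three omitted mediators sit in the residual. If an inert scale is correlated with the one that works, its slope on the outcome absorbs part of the active scale's effect. Multiplied by a non-zero arm effect on the inert scale, this gives an indirect effect whose true value is zero. Resampling the same model puts an interval around the wrong quantity.

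Both conditions are plausible here. Three of the four scales measure confidence or self-efficacy in the same patients at the same visits, and Aim 1a hypothesises that the mHealth arm will raise all four measures. False credit is therefore a real possibility precisely if the trial works as hoped. At stake is the interpretation of Aim 3: several scales could be reported as mediators when the data cannot distinguish them from one that truly is. The primary analysis is not affected.

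**Working it through.** The plan gives no power, effect size or correlation for mediation, so there is no figure to reproduce. The check is algebra plus simulation.

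**Inputs from the documents.** 400 patients (Study Population) and up to 10% deaths by six months (Data Analysis, missing data), so 400 x 0.9 = 360 before other dropout. Four mediators, modelled separately, product of coefficients.

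**Assumed.** 1:1 allocation; unit residual SDs; equal correlation rho between mediator residuals; arm effect a on each mediator; slope b1 for mediator 1 and 0 for the other three; direct effect c'. None of these values is in the documents.

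**Step 1, credit to an inert scale.** The single-mediator slope for inert scale k is rho x b1, so its indirect effect is a_k x rho x b1 instead of 0. With equal a this is rho times the active scale's a x b1. At a = b1 = 0.4 and rho = 0.5: 0.5 x 0.16 = 0.08, against 0.16 for the active scale.

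**Step 2, how often it is declared a mediator.** With a = 0.4, n = 360, change-score mediators, the plan's covariates, 1,500 trials per setting, and significance meaning a and b both below 0.05 (not a bootstrap):

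| rho | Inert scale significant, separate models |
|---|---|
| 0 | about 5% |
| 0.3 | 52-55% |
| 0.5 | 90-92% |
| 0.7 | 96-97% |

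In the parallel model the figure is about 4-6% throughout. With a = 0.3 the separate models give about 42-47% at rho 0.3 and 73-80% at 0.5-0.7, against 3-5% jointly. At least one false mediator then appears in 75-94% of trials (separate) against 9-13% (joint).

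**Step 3, dependence on the arm effect.** If the arm does not move the inert scale (a = 0), its mean indirect effect is about 0.00 and it is significant in 2-6% of trials, even at rho = 0.7. With a = 0.2 on the inert scales and rho = 0.5, it is significant in 42-44%.

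**Step 4, the sum.** With equal a the four separate effects sum to a x b1 x (1 + 3 x rho), against a total of c' + a x b1. The sum exceeds the total only if rho > (1/share - 1)/3, where share = a x b1/(c' + a x b1). At a = b1 = 0.4 and rho = 0.5 the sum is 0.16 x 2.5 = 0.40:

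| True mediated share | c' | Total | Sum/total at rho 0.5 | Threshold rho |
|---|---|---|---|---|
| 100% | 0 | 0.16 | 2.50 | 0 |
| 50% | 0.16 | 0.32 | 1.25 | 0.33 |
| 25% | 0.48 | 0.64 | 0.62 | 1.0 (never exceeded) |

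False credit itself does not need a large mediated share: at a = 0.3 and rho 0.5, with 50% or 25% mediated, inert scales were still significant in 76-77% of trials.

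**Step 5, price of the joint model.** Take a = 0.3 and a modest slope of 0.15. For the arm path, SE = 2/sqrt(360) = 0.105, z = 2.85, power about 0.81. For the slope in a separate model, SE = 1/sqrt(360) = 0.053, z = 2.85, power about 0.81; the product is about 0.66. In the joint model at rho 0.5 the slope variance is multiplied by (1 + 2 x 0.5)/[(1 - 0.5)(1 + 3 x 0.5)] = 1.6, so z = 2.85/sqrt(1.6) = 2.25, power about 0.61; the product is about 0.50. Simulation gave 49% joint against 65-66% separate, and 34% against 66% at rho 0.7.

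**The case against.** **The conditions are assumed.** No correlation is documented, and HF knowledge may be less related to the other three than they are to each other. A scale that the arm leaves alone gets no false credit. This stands: the claim is that an inert scale can appear to mediate, not that it will.

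**The sum.** A reader might infer that the reported effects will add up to more than the total effect. The documents do not support that: the plan does not sum them, and at a 25% mediated share the sum stays below the total at any correlation under 1.

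**The aim.** A reader might also infer that the plan is meant to show which part of the intervention to keep. Aim 3 explores whether these constructs mediate; they are patient-reported scales, not separable components, and no section proposes dropping anything on this basis.

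**The remedy is not neutral.** A parallel model assumes that no mediator causes another. If the arm raises knowledge, knowledge raises confidence, and confidence raises self-care, then knowledge does carry the effect. In simulations of that chain (path 0.5, knowledge effect 0.3 x 0.5 x 0.4 = 0.06), separate models found knowledge in 75% of trials and the parallel model in 3-5%. The documents do not exclude such a chain. It would also be wrong to say that power is unchanged: that is so at a slope of 0.4, where the arm path sets the power, but not at 0.15. Both points stand, and they rule out replacing the separate models.

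**Conclusion.** The concern holds in conditional form. Separate models cannot distinguish the four mediators from one another. If the mediator changes are correlated and the arm moves them all, an inert scale receives about rho times the active scale's indirect effect, and the planned bootstrap leaves this untouched. Across arm effects of 0.3-0.4 SD and an active slope of 0.4, with 360 patients, that means false mediation in roughly 42-55% of trials per inert scale at correlation 0.3 and 73-97% at 0.5-0.7. The separate effects are then not additive; their sum exceeds the total effect only when the mediated share is large enough for the correlation. Correlation, arm effects and slopes are all assumptions. The consequence is confined to an exploratory aim, but the improvement is cheap and worth making.

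**What to change.** In the mediator paragraph of Data Analysis:

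- Keep the four separate models.
- Add one pre-specified parallel model containing all four mediator changes, the four mediator baselines and the baseline outcome.
- Report each specific indirect effect and the total indirect effect, with bootstrap 95% intervals, beside the separate results.
- State that the separate effects are not mutually adjusted and must not be summed or ranked.
- Claim mediation by a particular scale only with the joint result shown.
- State that the parallel model assumes no mediator causes another, so a disagreement between the two analyses may reflect a chain as well as false credit.

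The cost is a few sentences and one further model on data already collected. The joint intervals will be wider, noticeably so at correlation 0.5 and above when mediator effects are modest, so a null joint result for one scale should not be read as proof that it plays no part.

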## **Data Analysis**

Data will be examined for completeness, outliers, and normality. Frequencies and percentages will be generated for screen failure reasons, for randomized participants, reasons for dropout and missing data. Descriptive statistics will be generated by intervention assignment and overall at 3 and 6 months. Baseline patient, caregiver, and system level characteristics will be compared according to intervention assignment to assess the success of the randomization; if there are imbalances, then consideration will be given to including the specific characteristic as a covariate to adjust intervention group comparisons. Continuous baseline variables will be compared using two-sample t-tests or nonparametric Wilcoxon rank sum & categorical variables will be compared using chi-square or Fisher's exact test.

Study Title: Innovative Care of Older Adults with Chronic Heart Failure (I-COACH): A

Comparative Effectiveness Clinical Trial

PI (researcher): [name], RD

Institution: University of Arkansas for Medical Sciences

Funding: PCORI Grant

For the Primary Outcome (Self-Care of Heart Failure Index, management subscale, Aim 1), we plan to compare arms in terms of change from baseline using a repeated measures mixed model analysis of covariance (ANCOVA) with an interaction between time and adjusting for baseline subscale score and other covariates such as age, race, education, and rurality. To address correlation arising from repeated measurements on the same subject over time, a random subject effect will be included in the model. For the primary endpoint, we will compare intervention effect at 3 months and at 6 months using contrasts (model-based t-tests) at a significance level of 0.025 (Bonferroni adjustment of alpha level of 0.05 for 2 comparisons). We will also use multiple imputation methods to address missing data (see below). Since scores  $> 70$  on the standardized scale have been used to indicate adequacy of self-care using a similar approach to the above, we will also analyze data as a binary endpoint in a repeated measures logistic model based on a generalized linear model framework.

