Plans to address missing data. Data collection procedures will be designed so that measures/instruments will not allow subjects to skip questions and assistance will be available to help complete the survey, if needed (e.g. may need to read to some participants if vision is problematic). We have built in travel resources to visit participants' homes to complete a measurement interval (baseline,-3,-6 month), and/or can split this task within 2 days if participants become fatigued, as needed. See Data Collection Procedures. Sensitivity analyses will be conducted to investigate the impact of missing data (in the case of attrition) on estimates. The above analyses based on mixed models assume data are missing completely at random, but we will also use multiple imputation techniques to model missing data patterns, which is appropriate when data are not missing at random. These results will be reported as well in keeping with an intent-to-treat approach which uses data from all randomized participants, even those lost to follow-up. We anticipate that up to 10% of participants may die by six months. To address any differential dropout rates between interventions, the composite endpoint approach will be assessed similar to what was done for QOL outcomes in the ELITE study; one-sided tests are required for the approach so we will split our alpha accordingly assuming the alternative hypothesis is that the enhanced mHealth care model results in better outcomes.

Study Title: Innovative Care of Older Adults with Chronic Heart Failure (I-COACH): A Comparative Effectiveness Clinical Trial  
PI (researcher): [name], RD  
Institution: University of Arkansas for Medical Sciences  
Funding: PCORI Grant

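### Multiple imputation is said to suit data not missing at random, but as described it assumes missing at random, so the 3- and 6-month primary contrasts have no not-at-random check

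*Combined protocol and SAP*

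**What the plan says.** The primary outcome paragraph of Data Analysis specifies a repeated measures mixed-model ANCOVA of the self-care management subscale, in which "a random subject effect will be included in the model". The 3-month and 6-month contrasts are each tested at 0.025. That paragraph says multiple imputation will also be used and refers the reader further on. The sensitivity paragraph says only that imputation methods will be looked into.

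The paragraph on plans to address missing data carries the substance:

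- On purpose: "Sensitivity analyses will be conducted to investigate the impact of missing data (in the case of attrition) on estimates".
- On the primary model: "The above analyses based on mixed models assume data are missing completely at random".
- On imputation: "multiple imputation techniques to model missing data patterns, which is appropriate when data are not missing at random".
- On the analysis set: "an intent-to-treat approach which uses data from all randomized participants, even those lost to follow-up".
- On deaths: "We anticipate that up to 10% of participants may die by six months".
- On unequal loss: "To address any differential dropout rates between interventions, the composite endpoint approach" will be assessed, with one-sided tests.

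None of these places gives an imputation model, a shift parameter, a reference-based rule, a pattern-mixture restriction or a tipping-point analysis.

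**The concern.** The plan treats imputation as the step that relaxes the mixed model's assumption. Standard multiple imputation does not do this. It draws missing scores from a model fitted to observed scores, which is valid under missing at random. That is the same condition under which a likelihood-based mixed model is valid. The plan therefore overstates what imputation does. It also understates the mixed model by tying it to missing completely at random, which is stricter than needed but harmless.

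The risk lies in interpretation. Patients are recruited around a hospital admission and the outcome is a questionnaire, so those managing poorly may be the ones who do not return it. If the imputed and mixed-model results agree, a report following this text would present the agreement as evidence against informative dropout, when both analyses share the assumption in question. Readers would not learn how far the dropouts must depart from missing at random before the primary conclusion changes.

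**Working it through.** **The plan's own figure.** The per-contrast level is 0.05 / 2 = 0.025, which reproduces. The two-sided critical value is 2.2414. The documents give no effect size, SD, correlation or non-death dropout rate, so everything below is illustrative.

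**Inputs from the documents.** 400 patients and up to 10% deaths by six months. With equal arms, 200 − 0.10 × 200 = 180 per arm.

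**Assumed inputs.** Deaths equal by arm and unrelated to score; scores in SD units with correlation 0.5 among baseline, 3 and 6 months; non-death 6-month missingness of 5, 10 or 20% per arm. In mHealth, missingness has a logit slope of −1 per SD of the unseen 6-month score (not at random). In control, the slope is −0.5 per SD of the 3-month score (at random).

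**Step 1: does imputation differ from the mixed model?** A random-intercept REML model (arm, time, arm × time, baseline) was compared with 20 imputations from arm, baseline and 3-month score, with and without one auxiliary variable. Bias in the 6-month contrast was taken at a true effect of 0.30 SD (2000 trials, Monte Carlo SE at most 0.001). The significance rates are at a true effect of zero (4000 trials) and count trials in which both analyses reach 0.025.

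| | 5% missing | 10% | 20% |
|---|---|---|---|
| Bias, mixed model | +0.032 | +0.061 | +0.117 |
| Bias, imputation, same variables | +0.032 | +0.061 | +0.117 |
| Bias, imputation, auxiliary correlated 0.3 | +0.030 | +0.057 | +0.110 |
| Bias, imputation, auxiliary 0.5 | +0.027 | +0.050 | +0.097 |
| Bias, imputation, auxiliary 0.7 | +0.020 | +0.037 | +0.073 |
| Both significant, same variables | 3.3% | 5.6% | 13.6% |
| Both significant, auxiliary 0.7 | 2.6% | 3.8% | 7.5% |

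The benchmark for the last two rows is 2.5%, with Monte Carlo SE √(0.025 × 0.975 / 4000) ≈ 0.25 points. With the same variables, the two estimates correlate at 0.998, 0.997 and 0.994, so their agreement carries almost no information about the mechanism. Auxiliaries, such as hospital and emergency visits from the medical record, reduce the bias but do not remove it.

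A separate simulation with 200 per arm gave the same picture. With about 13% (mHealth) and 10% (control) missing, regression and imputation under missing at random gave 0.384 and 0.383, against 0.303 with full data. With about 24% and 20% missing they gave 0.440 and 0.439, against 0.295.

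**Step 2: direction.** If missing scores lie δ SD below their missing-at-random prediction and f is the missing proportion, then

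bias = f(mHealth) × δ(mHealth) − f(control) × δ(control).

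With δ = 0.5 and 10% missing per arm:

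- mHealth only: 0.10 × 0.5 = +0.05 (simulated +0.049).
- Both arms: 0.05 − 0.05 = 0 (simulated 0).
- Control only: −0.05 (simulated −0.050).

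Delta-adjusted imputation with the correct shift was within 0.001 of the truth in every case examined.

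**Step 3: what a tipping-point analysis would report.** For an assumed observed effect of 0.30 SD and a shift in mHealth only, tipping shift = (0.30 − 2.2414 × SE) / f, with SE recomputed at the shift:

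- 5%: (0.30 − 2.2414 × 0.0978) / 0.05 = 1.62 SD
- 10%: (0.30 − 2.2414 × 0.0984) / 0.10 = 0.79 SD
- 20%: (0.30 − 2.2414 × 0.1028) / 0.20 = 0.35 SD

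**The case against.** Four points deserve weight.

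- **The composite analysis.** It is a planned response to death and unequal dropout, so the plan is not silent on informative loss. This stands. However, as described it is a one-sided test combining dropout with outcome, and it does not re-estimate the two mean contrasts under a stated not-at-random assumption or give a tipping point.
- **The wording about patterns.** It may mean pattern-mixture imputation. That is possible, but such a model is not identified without a restriction, and none is stated.
- **Size.** The main illustration takes one unfavourable direction. At 5% missing the error rates are close to nominal (2.6% with the strong auxiliary is within Monte Carlo error), and tipping shifts of 1.6 and 0.8 SD would suggest a fairly robust result. Marked harm appears near 20% non-death loss, which the documents do not predict. Home visits, help with completion, split sessions and a larger payment at month 6 should also limit loss. All of this stands, but retention measures reduce missingness without testing its mechanism.
- **Scope.** Only the 6-month contrast was quantified, and deaths were set aside, so the figures say nothing about the 3-month contrast or about scores after death.

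None of this rescues the stated justification.

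**Conclusion.** The concern holds and should be fixed. The sentence is wrong as written: followed literally, the attrition sensitivity analysis keeps the assumption it claims to relax, and no other planned analysis gives a not-at-random range for the primary contrasts. This conclusion comes from the text alone. The primary model, alpha and sample size are unaffected.

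The size rests on assumptions. The 6-month bias is about 0.03 SD at 5% and 0.12 SD at 20% non-death missingness if only mHealth loss is informative. It is zero or of opposite sign in other plausible cases. Which case applies is what the missing analysis would let readers judge.

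Two related gaps are missing detail rather than error. The imputation variables are not listed. Nor does the plan say how scores after death are treated in the imputation or in the mixed model, which implicitly extrapolates past death.

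**What to change.** 1. Correct the sentence according to what is meant. If standard imputation is intended, say that it and the mixed model both assume missing at random. If pattern-based imputation is intended, state its identifying restriction.
2. List the imputation variables, including any auxiliaries from the medical record.
3. Before unblinded analysis, prespecify one not-at-random sensitivity analysis of both the 3- and 6-month contrasts: either delta-adjusted imputation with the shift varied separately by arm and the tipping point reported, or reference-based imputation. Apply it to scores missing for reasons other than death.
4. State how scores after death are treated, consistently across the mixed model, the imputation and the composite analysis, and reconcile this with the commitment to use data from everyone randomized.

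The cost is SAP wording and a small amount of programming. No new data are needed, and sample size and alpha do not change.

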## Ethical Considerations

This study will be conducted in accordance with all applicable government regulations and University of Arkansas for Medical Sciences research policies and procedures. This protocol and any amendments will be submitted and approved by the UAMS Institutional Review Board (IRB) to conduct the study.

### Informed Consent & HIPAA Authorization

The formal consent of each subject, using the IRB-approved consent form, will be obtained before that subject is submitted to any study procedure. All subjects for this study will be provided a consent form describing this study and providing sufficient information in language suitable for subjects to make an informed decision about their participation in this study. The person obtaining consent will thoroughly explain each element of the document and outline the risks and benefits, alternate treatment(s), and requirements of the study.

The consent process will take place in a quiet and private room in-person or verbally by telephone, and subjects may take as much time as needed to make a decision about their participation. Participation privacy will be maintained and questions regarding participation will be answered. No coercion or undue influence will be used in the consent process. This consent form will be signed (written or Electronic consent) by the subjects if this is an in-person interaction, and by the person obtaining the consent. If this is a telephone consent, the Research Assistant will document "telephone consent" on the form.

A copy of the signed, or telephone informed consent document and HIPAA authorization will be given, emailed, or mailed to the participant, and the informed consent process will be documented in the research record.

In light of the COVID-19 pandemic, we may need to perform informed consent and obtain HIPAA authorization on some subjects verbally, using the telephone. For example, because of COVID-19, caregivers are most often not in the patient's hospital room and may only be allowed to pick up the patient outside of the building, we would not have a in person interaction with the caregiver at all. Additionally, if the HF patient is recommended to quarantine, although he/she would be in the hospital, we may need to contact the participant by telephone to limit the in-person interaction time.

The verbal consent & HIPAA authorization of subjects, using the IRB-approved telephone script, will be obtained before the subject is allowed to participate in any study procedure. The person obtaining consent and HIPAA authorization will thoroughly explain each element of the documents, especially outlining the risks and benefits, alternate treatment(s), and requirements of the study. Subject consent and HIPAA

Study Title: Innovative Care of Older Adults with Chronic Heart Failure (I-COACH): A Comparative Effectiveness Clinical Trial  
PI (researcher): [name], RD  
Institution: University of Arkansas for Medical Sciences  
Funding: PCORI Grant

authorization will be documented on the informed consent process note in the subject research file.

The research team member obtaining consent and HIPAA authorization will document the consents by indicating a proxy signage of the “*telephone consent*” of “participant name” by “research team member’s name”, with “time and date”. A copy of these forms will be mailed to the participant. (This alternative to an in-person consent will also limit contact with potentially contaminated documents and reduce burden on patient participant and caregiver.)

